1.3 SCHEDULE OF ACTIVITIES (SOA)

	Screening (V1) Day -42 to -1	Baseline / Random. Visit 2, Day 1	Study Visit 3 Day 7 +3 dav	Study Visit 4 Day 14 + 3 dav	Study Visit 5 Day 21 +3 dav	Study Visit 6 Day 28 +3 dav	Study Visit 7 Day 56 +15 dav	Study Visit 8 Day 84 +15 dav	Study Visit 9 Day 112 +15 dav	Study Visit 10 Day 140 +15 dav	Study Visit 11 Day 168 +15 dav	Study Visit 12 Day 196 +15 dav	Study Visit 13 Day 224 +15 dav	Study Visit 14 Day 252 +15 dav	Study Visit 15 Day 280 +15 dav	Study Visit 16 Day 308 +15 dav	End of study V17 Day 336 +15 dav	Phone followup V18 Day 350 +/-5 dav	Safety assess. V19 Day 365 +/-5 dav
Procedures																			
Visit type	S	S	SL	SL	SL	SL	SL	S	SL	SL	S	SL	SL	S	SL	SL	S	P	SL
Informed consent	X																		
Demographics	X																		
Medical history	X																		
Randomization		X																	
Administer study intervention		X																	
Dispense study drug		X						X			X			X					
Retrieve study drug								X			X			X			X		
Conclusion of study																			X
Conc. Medication review	X	X						X			X			X			X		
Physical exam	X	X						X			X			X			X		
Vital signs, height & weight	X	X						X			X			X			X		
MSA criteria	X																X		
MoCA	X	X ^e															X		
UMSARS	X	X ^e						X			X			X			X		
Sirolimus levels in blood ^d			X	X	X	X	X	X	X	X	X	X	X	X	X	X	X		
Complete blood count	X	X ^e	X	X	X	X	X	X	X	X	X	X	X	X	X	X	X		X
Comprehensive metabolic ^a	X	X ^e	X	X	X	X	X	X	X	X	X	X	X	X	X	X	X		X
CPK	X	X ^e	X	X	X	X	X	X	X	X	X	X	X	X	X	X	X		X
Lipid panel	X	X ^e	X	X	X	X	X	X	X	X	X	X	X	X	X	X	X		X
Urinalysis	X	X ^e	X	X	X	X	X	X	X	X	X	X	X	X	X	X	X		X
24-hour urine collection	X	X ^c					X	X	X	X	X	X	X	X	X	X	X		X
Pregnancy test ^b	X																		
HIV testing, hepatitis B and C testing, QuantiFERON®	X																		
Nasal swab PCR COVID-19	X																		
EKG	X	X ^e						X			X			X			X		
Adverse event review			X	X	X	X	X	X	X	X	X	X	X	X	X	X	X	X	X
Brain MRI		X																	X
Retinal OCT		X																	X
Blood sample for exosomes		X									X						X		
Complete Case Report Forms	X	X	X	X	X	X	X	X	X	X	X	X	X	X	X	X	X	X	X

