This study will include a placebo group in 3:1 proportion. Our reason for including a placebo arm is to facilitate blinding to treatment assignment and also to permit a descriptive assessment of the validity of the assumed change in UMSARS over time in the historical control group; the placebo group *will not* be used for primary outcome purposes with the active treatment arm.

This will be single-center study performed at the NYU Dysautonomia Center, one of the leading centers in the diagnosis and management of MSA. [name], the director of the Center, is the PI of the international Natural History Study of MSA, within the NIH-funded Rare Diseases Autonomic Disorders Consortium. NYU has the infrastructure and personnel in place to undertake this study and is experienced in the conduct of clinical trials. NYU is in a position to rapidly commence the study and conduct the study efficiently. We will review the option of adding additional sites if recruitment in the first 15 months is slow. Our aim is to complete recruitment within 24 months from commencement of the study.

Eligible participants, who signed the approved informed consent form at the screening visit, will initially receive sirolimus 2 mg/day (one 2-mg capsule/day) or matching placebo in a 3:1 fashion. The dose of sirolimus will be adjusted throughout the trial based on sirolimus blood levels and the presence of drug-related adverse events. The maximum dose of sirolimus will be 6 mg/day (three 2-mg capsules/day) or matching placebo. Patients receiving placebo will undergo analog sham level measurements and the number of capsules will be also adjusted to maintain the blinding of the trial. Patients will receive active agent or placebo for 48-weeks.

Participants will be evaluated at study clinic by the investigator at the screening visit and at baseline visit and will return to the clinic at Day 84 (month 3), Day 168 (month 6), Day 252 (month 9), and Day 363 (month 12) (+/- 10 days) of beginning the study treatment.

Detailed study plan

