Screening visit (Visit -1, Day -42 to -1): Prior to performing any study activities/evaluations, the potential participant must be thoroughly informed about all aspects of the study, including scheduled study visits and activities, and must sign the informed consent. A signed copy of the approved informed consent will be given to the participant. Screening procedures will include demography, medical history, inclusion and exclusion criteria assessment, MSA diagnosis confirmation, physical examination, vital signs & height/weight, EKG, concomitant medication, adverse events, laboratory and safety testing (serum pregnancy test, if applicable, CBC, CMP, CPK, urinalysis and 24-hour urine collection (to quantify the protein/creatinine ratio), lipid panel, HIV, hepatitis B and C serologies, and QuantiFERON®), and UMSARS scale.

COVID-19 nasal swab PCR will be performed at screening. If negative, enroll patient. If positive, patient should be quarantined for at least 2 weeks and consult with their PCP to determine if any treatment is necessary. Participants can be re-screened after 4 weeks with a second nasal swab PCR for COVID-19. If negative, the patient can be enrolled. If still positive, patient will be definitely excluded and recommended continued follow-up with an infectious disease specialist.

If the subject has laboratory tests and EKG results available performed within 90 days before the screening date, it will be allowable to use these for the screening visit.

Safety labs should be performed at least 3 hours after a light (low fat) breakfast.

There will be a screening period of up to 42 days.

Baseline visit (Visit 1, Day 1): The following tasks/procedures will be performed at the clinic during the baseline visit:

- EKG
- MoCA
- Concomitant medications
- Physical examination
- Vitals signs
- CBC, CMP, CPK (8 ml of blood) urinalysis
- Lipid panel
- Dispensing of study medication

- UMSARS scale
- Blood sample for exosomes (2 ml of blood)
- Retinal optical coherence tomography
- 24-hour urine collection. This test should be performed only if the baseline visit occurs > 30 days from the screening visit.

If the baseline visit is performed less than 14 days from the screening visit the following procedures can be foregone, and the results will be assumed to be similar to those obtained at the screening visit:

- EKG
- MoCA
- CBC, CMP, CPK (8 ml of blood), urinalysis
- Lipid panel
- UMSARS scale

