Participants will be dispensed study medication during the baseline visit. In case this is not possible, participants will be mailed the study medication within 30 days of the baseline visit.

The case report forms will note the date when the subject will start the study medication.

Participants will also undergo a non-contrast brain MRI with specific sequences to evaluate the diffusion at the putamen and pons. The brain MRI will be performed at the NYU Center for Biomedical Imaging. There will be a brain MRI period of up to 7 days after the baseline visit (i.e., subjects must be scanned within 7 days after the baseline visit).

Scheduled site visits: assessment of the primary outcome measure and safety labs will be conducted on-site at study visits at Visit 8 (month 3 after initiation of study drug), Visit 11 (month 6 after initiation of study drug), Visit 14 (month 9 after initiation of study drug), and Visit 17 (month 12 after initiation of study drug) (+ 15 days). We will accept a visit window of 15 days after the target date. The following tasks will be performed:

- EKG
- Concomitant medications
- Adverse event recording
- Physical exam
- Vital signs
- UMSARS scale
- CBC, CMP, CPK (8 ml of blood) and urinalysis with 24-hour urine collection
- Lipid panel
- Sirolimus levels in blood (5 ml of blood)
- Retrieve study drug
- Dispense study drug. If dispensation of study drug is not possible during the visit, the study drug will be mailed within 15 days.

Safety Laboratory Visits: Assessment of safety will be conducted on-site or locally at study visits 7 days (with a window of 3 days after the target date) after initiation of study drug (Study Visit 3), and 7 days after the patient has increased dose of study drug (i.e., Study Visit 4, Study Visit 5 and Study Visit 6, with

a window of 3 days after the target date) during the first month of study drug treatment. We will accept a visit window of 3 days after the target date of these visits.

Assessment of safety visits will also occur on-site or locally on Month 2 (Study Visit 7, this visit may be skipped in previous visits were delayed, to ensure that Visit 8 occurs at Month 3), Month 4 (Study Visit 9), Month 5 (Study Visit 10), Month 7 (Study Visit 12), Month 8 (Study Visit 13), Month 10 (Study Visit 15), and Month 11 (Study Visit 16). We will accept a visit window of 15 days before or after the target date of these visits.

The following safety laboratory assessments will be performed:

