9.4.2 ANALYSIS OF THE PRIMARY EFFICACY ENDPOINT

The primary outcome endpoint (UMSARS total score) will be analyzed by comparing the mean decline in total UMSARS score in the active sirolimus group (UMSARS total score at week 48 minus UMSARS total score at baseline) with the pre-specified fixed value of 8.6 (SD: 9.2) using a one-sample t-test. If the difference between the fixed value of 8.6 minus the UMSARS total score in the active sirolimus group is 4 or less, the null hypothesis will be rejected, indicating futility.

Missing data will be addressed by using a regression-based multiple imputation model (78)

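### The primary endpoint sets a raw UMSARS change over a variable, partly untreated interval against a fixed 12-month benchmark, with no time zero and no adjustment

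*Combined protocol and SAP*

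**What the plan says.** **Start of the interval.** Section 4.1 (baseline visit) allows the screening UMSARS to serve as the baseline score: "If the baseline visit is performed less than 14 days from the screening visit the following procedures can be foregone". UMSARS is on the list of such procedures, and its screening value then stands in for baseline. Footnote e of the Schedule of Activities (1.3) sets the limit at 15 days instead.

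**Start of drug.** Dispensing at the baseline visit is the rule. Where that fails, Section 4.1 says "participants will be mailed the study medication within 30 days of the baseline visit". This limits mailing; the text sets no limit on the date of the first dose. The date is captured: "The case report forms will note the date when the subject will start the study medication". Section 9 makes no use of it, and no new UMSARS is required at drug start.

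**End of the interval.** Four places describe the final visit:
- Section 4.1, overview: "Day 363 (month 12) (+/- 10 days) of beginning the study treatment".
- Section 4.1, scheduled site visits: "Visit 17 (month 12 after initiation of study drug) (+ 15 days", the window running only after the target date.
- Section 4.1, end of study visit: 15 days before or after the target date.
- Section 1.3: "End of study V17 Day 336 +15 dav", with baseline on Day 1.

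**Analysis.** Section 9.4.2 defines the change as "UMSARS total score at week 48 minus UMSARS total score at baseline" and compares the sirolimus mean with 8.6 by a one-sample t-test. Section 9.2 derives 8.6 from two cohorts measured at 12 months. Sections 4.1 and 4.2 exclude the placebo arm from the primary comparison.

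**The concern.** A single-arm comparison with a fixed number works only if the treated change and the benchmark cover the same length of time. Here one side is a 12-month figure. The other is whatever interval results from a possibly older baseline score, a possibly late drug start and a final visit with conflicting anchors.

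In a two-arm test, placebo participants would face the same delays and most of the distortion would cancel. In this design nothing absorbs it. Rejecting the null means declaring futility, so untreated progression inside the interval counts against sirolimus and could help discard a drug that meets the plan's own criterion of promise. A rating at 48 weeks set against a 12-month figure has the opposite effect and makes futility harder to declare.

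**Working it through.** **Inputs.** Benchmark 8.6 points, SD 9.2, measured at 12 months; required benefit 4 points, so threshold 4.6; one-sided alpha 0.05; 38 evaluable on sirolimus (all Section 9.2). Assumptions: linear progression; a drug with exactly the 4-point benefit; the t-test at one-sided 0.05 decides.

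**The plan's own figures.** The weighted mean is (96 × 7.5 + 50 × 10.8)/146 = 8.63 and the weighted SD is (96 × 8.4 + 50 × 10.7)/146 = 9.19. Both match the plan. The sample size of 38 is not reproduced: the stated inputs give 33 (normal) or 35 (t). It is kept below as the plan's evaluable number; at 38 the power is 0.84.

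**Daily rates.** Untreated: 8.6/365 = 0.0236 points. On drug: 4.6/365 = 0.0126 points.

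**Effect of a delay, visit at month 12 on drug.** A 30-day delay adds 30 × 0.0236 = 0.71 points for that participant, 18% of the 4-point margin. If a share f is delayed, the arm mean shifts by 0.71f. False futility is the upper tail of a noncentral t with 37 degrees of freedom and noncentrality shift × √38/9.2.

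| Share delayed 30 days (assumed) | Shift | False futility |
|---|---|---|
| 0% | 0 | 5.0% |
| 10% | 0.07 | 5.5% |
| 25% | 0.18 | 6.3% |
| 50% | 0.35 | 7.9% |
| 100% | 0.71 | 11.9% |

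**Effect of the visit anchor.** Expected mean = 0.0236 × untreated days + 0.0126 × days on drug, compared with 4.6. All participants are treated alike in each row.

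| Untreated days | Days on drug | Mean | Against 4.6 | False futility |
|---|---|---|---|---|
| 0 | 336 | 4.23 | −0.37 | 3.0% |
| 30 | 336 | 4.94 | +0.34 | 7.8% |
| 30 | 363 | 5.28 | +0.68 | 11.6% |
| 30 | 306 (visit 336 days after baseline) | 4.56 | −0.04 | 4.8% |

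In the last row the untreated month and the short interval almost cancel. The direction of the net error therefore depends on which anchor is used and how many start late.

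**What scaling by actual days does.** With 30 untreated and 365 treated days the change is 5.31; scaled, 5.31 × 365/395 = 4.90, so the excess falls from 0.71 to 0.30 (7.4%). With 30 untreated and 336 treated days, 4.94 × 365/366 = 4.93, so the excess goes only from 0.34 to 0.33. With no delay and 336 days, 4.23 × 365/336 = 4.60, and the 5% rate is restored. Scaling corrects the length of the interval, not its untreated share.

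**What subtraction does.** Removing 0.71 first and scaling the rest by days on drug gives (4.94 − 0.71) × 365/336 = 4.60. Under these assumptions this removes both errors.

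**The case against.** The strongest reply is that the problem is rare and partly self-correcting. Mailing is the exception, 30 days is its limit, and at 10% or 25% delayed the error rate is 5.5% or 6.3%, close to nominal. A 30-day delay followed by 48 weeks on drug gives 366 days in total, about the benchmark's own length. Placebo participants follow the same provisions and provide a descriptive check on the assumed change. Much of this stands: the effect is small unless late starts are common. But matching total length does not make the untreated month a treated one (4.94 against 4.6), and 14 placebo participants are a weak check.

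Two stronger readings are tempting, and the documents support neither.
- A reader might infer that the error always runs towards futility. The windows that open before the target date, and a Day 336 visit against a 12-month figure, shorten the interval and favour sirolimus.
- A reader might add screening carry-over (15 days), mailing delay (30) and late visit (15) into 60 untreated days, giving 1.41 points and 24% false futility. The last 15 days are on drug, so the sum is 45 × 0.0236 + 15 × 0.0126 = 1.25 points and 20.5%. Even that needs every participant at all three limits at once, which nothing in the documents suggests.

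**Conclusion.** The concern holds as a gap in the definition of the primary endpoint. The interval is not fixed, its anchors conflict, part of it may be untreated, and the analysis ignores all of this. The shift is 0.71 points per participant delayed 30 days and rated at month 12 on drug. Across the scenarios in the two tables, false futility runs from 3.0% to 11.9% around the planned 5%, and is likely near the middle unless late starts are frequent.

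These figures rest on linear progression, SD 9.2, n=38 and an assumed share delayed, which the documents do not give. They also take the t-test as the decision; 9.4.2 follows it with a sentence that can be read as a rule on the point estimate, to which these rates would not apply. The matter is worth settling before analysis, since an adjustment chosen after the results are known would be post hoc.

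**What to change.** 1. Reconcile the final-visit anchors and windows in Section 1.3 and the three places in Section 4.1, along with the 14- and 15-day limits for carrying over the screening UMSARS. State time zero for the endpoint.
2. In 9.4.2, for participants with a final-visit UMSARS, scale the change by the actual days between the two ratings to the benchmark's 12 months. Keep the raw change as supportive.
3. Leave early terminations to the planned multiple imputation. Section 9.3 admits participants with as little as 3 months of drug; extrapolating a 3-month change to 12 months would multiply its measurement error about fourfold. The synopsis wording that allows the last available date should be aligned with this.
4. Report the distribution of days from the baseline rating to the first dose.
5. Because scaling leaves untreated days in, add a sensitivity analysis that subtracts 8.6/365 points per untreated day and scales the remainder by days on drug, or one that excludes delayed starters.

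Cost: a few derived variables from rating dates and the drug start date already recorded, with no added visits or participants. Scaling assumes roughly linear progression over a year and adds slight variance. The subtraction borrows the benchmark's own rate, and the exclusion loses participants, so both are supportive only.

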- If sirolimus levels are < 5 ng/mL, the participant will be instructed to take sirolimus 2 mg two capsules daily (4 mg total dose) or matching placebo; sirolimus levels will be then measured again 7 days after the patient began taking 4 mg/day (+ 3 days). If sirolimus levels are between 5 and 20 ng/ml, the subject will continue with that dose until the next measurement of sirolimus levels on Visit (+ 3 days).
- If sirolimus levels are > 30 ng/ml with one capsule/day, the subject will be excluded from the trial due to the high risk of adverse events.

Subjects who were instructed to increase their dose to 4 mg will undergo another measurement of sirolimus levels 7 days after the previous dose adjustment (+ 3 days):

- If sirolimus levels are < 5 ng/mL, the participant will be instructed to increase sirolimus to 2 mg three capsules daily (6 mg total dose) or matching placebo. Sirolimus levels will be then measured 7 days after the patient began taking 6 mg/day (+ 3 days).
- If sirolimus levels are between 5 and 20 ng/ml, the subject will continue with that dose until the next measurement of sirolimus. If the sirolimus levels are > 20 ng/ml, the subject will be instructed to go back to the 2 mg/day dose and continue with that dose until the next measurement of sirolimus levels.

From Visit 3 to Visit 6, sirolimus level blood draw will take place 7 days (+3 days) after the previous dose adjustment has taken place (i.e., 7 days after the patient started taking the adjusted dose).

From Visit 7 onwards, subjects will be instructed to increase or decrease their sirolimus dose (between a min dose of 2 mg/day to a max dose of 6 mg/day) depending on blood levels (target: 5-20 ng/ml) and the emergence of adverse events.

Expected dose-limiting effects requiring sirolimus dose reduction are:

- Grade 2 stomatitis or mucositis
- Grade 2 lymphedema
- Grade 2 proteinuria
- Grade 2 renal failure
- Grade 3 pneumonitis
- Grade 2 diarrhea

Every attempt will be made to maintain the participant on the full dose. If the participant is unable to maintain the full dose, the minimum acceptable dose is 2 mg once a day. An attempt will be made to increase the dose with a re-challenge at a later date. Capsules should be swallowed whole with a glass of water or may be taken with food to minimize gastrointestinal side effects.

To maintain investigator and subject blinding during the clinical trial, the results of the sirolimus

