6.2.2 FORMULATION, APPEARANCE, PACKAGING, AND LABELING

Sirolimus capsules (2 mg) and matching placebo capsules will be packaged in tight, light-resistant bottles as defined in the US Pharmacopeia. Sufficient bottles for 3 months of study will be packed for each participant, taking into consideration the potential increases in sirolimus dose after measuring sirolimus levels in blood. Each bottle label will bear the site number, investigator's name, participant number and the bottle number which comprises the participant number followed by a sequential number (01, 02, 03, 04, etc.).

The label on the bottles will include a fixed information section (to include the product name, storage conditions, instructions etc.) and variable information section. The variable information section will include 3 parts: 2 detachable parts, which will be attached to the participant's file upon bottle dispensing and 1 part to remain on the bottle. The variable information section will include the following variable data: site number, investigator name, participant number, bottle number, batch code and expiration date (all to be pre-printed on the label) and blank field for visit number to be manually filled in by the Investigator or designee upon provision of bottle to the participant.

Study drug supplies will be kept at the Total Town Compounding pharmacy, in a secure, limited-access, temperature/humidity-controlled area and a temperature/humidity log will be maintained. Only authorized personnel will have access to the study drug. The Total Town Compounding pharmacy personnel will be responsible for correct storage and handling of the study drug. The study drug bottles will be dispensed to the participant at the study site at each study visit starting at baseline visit (except for termination visit). The site number and investigator's name will be pre-printed on the bottle label. Since the participant number is pre-printed on the bottle label, assigning the right bottles to the

participants is straightforward. After assigning a bottle to the participant, the site personnel should fill in the visit number on the label of the dispensed bottle as well as on the detachable parts that would be attached to the participant's file.

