At each dispensing visit, the participant will be dispensed with the study drug with the participant's number printed on the label. Any of the bottles designated for a participant can be dispensed in each of the dispensing visits. The bottle with the bottle number "participant # -R" is designated to replace damaged or lost bottles and should be used only for replacement.

In case a replacement bottle is required, the Total Town compounding pharmacist will be notified.

Participants will be instructed to return all used empty bottles and unused study drug at each visit.

The study coordinator is responsible for performing study drug accountability at the site and the accountability of the returned study drug.

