7.2 PARTICIPANT DISCONTINUATION/WITHDRAWAL FROM THE STUDY

Participants are free to withdraw from participation in the study at any time upon request. An investigator may discontinue or withdraw a participant from the study for the following reasons:

- Pregnancy
- Significant study intervention non-compliance
- If any clinical adverse event (AE), laboratory abnormality, or other medical condition or situation occurs such that continued participation in the study would not be in the best interest of the participant
- Disease progression which, in the opinion of the investigator, requires discontinuation of the study intervention
- If the participant meets an exclusion criterion (either newly developed or not previously recognized) that precludes further study participation
- Participant unable to receive study drug for 15 days or more.

The reason for participant discontinuation or withdrawal from the study will be recorded on the electronic Case Report Form (CRF). Subjects who sign the informed consent form and are randomized but do not receive the study intervention may be replaced. Subjects who sign the informed consent form, and are randomized and receive the study intervention, and subsequently withdraw, or are withdrawn or discontinued from the study, will not be replaced.

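### When resupply is mailed after Visits 8, 11 or 14, participants have already returned their unused drug, so a permitted delay interrupts treatment and collides with the 15-day withdrawal reason

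*Combined protocol and SAP*

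**What the plan says.** **Return of drug.** Section 4.1 and the Schedule of Activities (Section 1.3) list both retrieval and dispensing of study drug at Visits 8, 11 and 14. Section 6.2.2 makes the return complete: "Participants will be instructed to return all used empty bottles and unused study drug at each visit".

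**Resupply.** The default is in person: "The study drug bottles will be dispensed to the participant at the study site at each study visit starting at baseline visit" (Section 6.2.2). The fallback in Section 4.1 is: "If dispensation of study drug is not possible during the visit, the study drug will be mailed within 15 days". On its wording this limits when drug is posted, not when it arrives. On quantity, Section 6.2.2 says "Sufficient bottles for 3 months of study will be packed for each participant", with an allowance for possible dose increases.

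**Levels and dose.** A level is drawn at each of these site visits and again at Visits 9, 12 and 15. Section 6.1.2 says: "From Visit 7 onwards, subjects will be instructed to increase or decrease their sirolimus dose", depending on blood levels and adverse events.

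**Windows.** For the site visits Section 4.1 says: "We will accept a visit window of 15 days after the target date". For Visits 9, 12 and 15 the Schedule of Activities gives +15 days, while the Section 4.1 text allows 15 days either side.

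**Withdrawal.** Section 7.2 lists, among the reasons for which an investigator may withdraw a participant: "Participant unable to receive study drug for 15 days or more".

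**The concern.** If every remaining capsule goes back and the next supply is posted later, the participant has nothing to take in between. The interruption then comes from the supply rules, not from the patient or the drug's tolerability.

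Three things are at stake.

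- **Two rules collide.** A delay that Section 4.1 permits can satisfy a withdrawal reason in Section 7.2.
- **A level may be misread.** A low value drawn during or soon after a supply gap looks the same as a low value on continuous treatment. The documents do not say how to interpret a level after an interruption, or that the pharmacist who acts on it is told of the gap.
- **Direction of any bias.** The primary test sets the sirolimus arm against a fixed historical value. If the drug works, lost exposure can only move the result toward futility.

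**Working it through.** The plan states no gap length and no time back on drug before the next level, so there is no figure of its own to reproduce. The check is visit-day arithmetic.

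**Inputs.** Site visits: Days 84, 168 and 252. Next levels: Days 112, 196 and 280, each 28 days later (Section 1.3). Latest posting: 15 days after the site visit (Section 4.1). Transit time: not given.

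**1. Length of the gap.** Drug returned on Day 84 and posted on Day 84 + 15 = Day 99 leaves 15 elapsed days with no supply, before transit. In missed doses, this is 14 if the doses on Days 84 and 99 are both taken. One day in the post makes it 15. A full permitted delay therefore meets the Section 7.2 reason with zero transit when counted in elapsed days, and with one day of transit when counted in missed doses.

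**2. Time back on drug at the next level, nominal days.** Level day − (visit day + 15 + transit):

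- Zero transit: 112 − 99 = 13 days. The same holds for 196 − 183 and 280 − 267.
- Assumed transit of 3, 5 or 7 days: 10, 8 or 6 days.

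For comparison, the plan draws a level 7 days after a dose adjustment. The level taken at the site visit itself precedes any gap.

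**3. Within the Schedule of Activities windows.** Let the site visit be *i* days late and the next visit *j* days late, each from 0 to 15. With posting on day 15 and zero transit, time back on drug is 13 + *j* − *i*.

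- Range: 13 + 0 − 15 = −2 days (level drawn before posting: visit Day 99, posting Day 114, level Day 112) to 13 + 15 − 0 = 28 days.
- Under 7 days requires *i* − *j* ≥ 7. That is 9 + 8 + … + 1 = 45 of 16 × 16 = 256 day pairs (17.6%).
- Zero or fewer days requires *i* − *j* ≥ 13. That is 3 + 2 + 1 = 6 of 256 (2.3%).

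These are shares of permitted date pairs, given the longest delay. They are not probabilities.

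**4. With the Section 4.1 text window of ±15 days.** The next visit can be as early as Day 97. A site visit on Day 99 followed by a level on Day 100 gives 100 − 114 = −14 days. The range is −14 to 28.

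**5. Would the compliance check detect it?** Three full 15-day gaps are 45 of 336 days (13.4%), leaving 86.6%. Section 6.4 sets non-compliance at under 75% and does not say how days without supply count.

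**6. Illustrative upper bound on the primary test.** Assume n = 38, SD 9.2, a one-sided 5% one-sample t-test against 4.6, a true 4-point benefit, every participant affected, and benefit proportional to days on drug. The mean shifts by 4 × gap/336:

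| Days lost per participant | Shift (points) | Chance of declaring futility |
|---|---|---|
| 0 | 0 | 5.0% |
| 15 | 0.18 | 6.3% |
| 30 | 0.36 | 7.9% |
| 45 | 0.54 | 9.8% |

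**The case against.** **Mailing is a fallback.** In-person dispensing is the rule, 15 days is the limit for posting, and no frequency is given. A reader might infer that the schedule routinely creates gaps just before a dose-driving level. The documents do not support that: at nominal days the next level comes 13 days after the latest posting, longer than the 7 days the plan uses after a dose change. A level during or soon after the gap needs a late site visit, an early laboratory visit or slow post on top of a long mailing delay. This objection stands and limits the point to a contingency.

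**Longer gaps.** One might add a 15-day-late visit to a 15-day mailing delay, reach Day 114, and subtract a pack of 84 to 90 days to get 24 to 30 days without drug. That overlooks the allowance for dose increases in Section 6.2.2. Participants whose dose has not risen should have spare capsules until the visit. The longer figure applies only to someone who has used the whole pack, so it is not a general one.

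**Dose and withdrawal are not automatic.** Adjustment from Visit 7 also weighs adverse events and is recommended by an unblinded pharmacist. Section 4.1 allows unscheduled levels. Section 7.2 says an investigator may withdraw a participant, not must. All this is true, but judgement needs the facts. Section 10.1.6 provides monthly calls that include the pharmacist, yet the topics listed for the investigator are recruitment, screen failures, withdrawals and adverse events.

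**Effect on the primary result.** Nothing supports benefit proportional to days on drug. Section 2.2.1 reports immunosuppression lasting up to 6 months after stopping in some studies. This stands against using the futility percentages as an expected effect.

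**Conclusion.** The point holds as a contingency written into the plan. When the next supply is not dispensed at Visit 8, 11 or 14, following Sections 4.1 and 6.2.2 as written can leave a participant without drug for up to 15 days plus transit. That reaches the Section 7.2 reason, so one rule can trigger the other. This part rests only on the text and, if missed doses are counted, on one day in the post.

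The effect on levels is possible but not usual: nominally 13 days back on drug, with a permitted range of −2 to 28 days under the Schedule of Activities and −14 to 28 under the Section 4.1 text. The gap in the plan is that no instruction covers a level after an interruption and no route carries supply dates to the pharmacist.

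A reader might take the rise in false futility from 5% to between 6.3% and 9.8% as the expected damage. It is only an illustrative upper bound, because it needs every participant to have the stated loss and benefit to be proportional to exposure. Since the frequency of mailing is unknown, no expected effect on the primary result can be quoted.

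**What to change.** 1. In Sections 4.1 and 6.2.2, retrieve remaining capsules only once the next supply is in the participant's hands. When drug is mailed, the participant keeps the current bottle and accountability is carried to the next visit.
2. Send the start and end dates of any supply gap to the independent pharmacist with each level, for both arms.
3. Reconcile the mailing allowance (4.1), the level-driven adjustment (6.1.2) and the 15-day reason (7.2), so that a delay the plan permits does not conflict with either of the others. Align the windows for Visits 9, 12 and 15 between Sections 1.3 and 4.1. State how a level after an interruption is handled and how days without supply count in the Section 6.4 compliance figure. Which dose or withdrawal rule applies is for the sponsor and investigators to settle.

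The cost is protocol and pharmacy wording, one more data item sent with each level, and slightly more complex drug accountability when a bottle is carried over a visit.
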